7.2 Treatment(s) to be administered

Lacosamide will be administered orally bid (at approximately 12-hour intervals in the morning and in the evening). Administration of oral solution by feeding tube is permitted for subjects who are unable to swallow the oral solution. At the end of the Baseline Period and completion of Visit 2, subjects who meet the eligibility criteria will commence a 6-week Titration Period (LCM dosing flexibility allowed based on tolerability).

As described in Section 5.1, subjects will initiate treatment with LCM oral solution at 2mg/kg/day, or LCM tablets at 100mg/day based on body weight. The dose will be titrated to a level to optimize tolerability and seizure control, not to exceed 12mg/kg/day (oral solution) for subjects weighing <50kg, or 600mg/day (tablets/oral solution) in subjects weighing ≥50kg. Subjects will increase the LCM dose in a stepwise fashion on a weekly basis to optimize tolerability and seizure control (see Figure 5-1 and Figure 5-2). During the Titration Period only, back-titration is permitted.

The planned doses for each week of the Titration Period for subjects taking the LCM oral solution and tablet formulations are displayed in Table 7-1.

Table 7-1: Lacosamide dose titration during the Titration Period

Body weight category (formulation)	Flexible doses for the Titration Period by study week					
	Week 1	Week 2	Week 3	Week 4	Week 5	Week 6
<50kg (oral solution)	2mg/kg/day	4mg/kg/day	6mg/kg/day	8mg/kg/day	10mg/kg/day	12mg/kg/day
≥50kg (tablets/oral solution)	100mg/day	200mg/day	300mg/day	400mg/day	500mg/day	600mg/day

LCM=lacosamide

Note: Subjects weighing ≥50kg who are unable or unwilling to swallow tablets can be dispensed LCM oral solution instead.

After completion of Week 1, investigators will assess whether a subject would tolerate a further dose increase or whether a subject should hold the Week 1 dose for a longer duration. This hold will be at the investigator's discretion. The flexible LCM dosing over the remainder of the Titration Period is outlined in Table 7-2.

Table 7–2: Flexible LCM dosing during the Titration Period

Body weight category (formulation)	Target dose increase/week ^a (titration)	Dose decrease per back-titration step		Subsequent dose increase ^b (dose increase after back -titration step)	
		Min	Max	Min	Max
<50kg (oral solution)	2mg/kg/day	1mg/kg/day	2mg/kg/day	1mg/kg/day	2mg/kg/day
≥50kg (tablets/oral solution)	100mg/day	50mg/day	100mg/day	50mg/day	100mg/day

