LCM=lacosamide; Max=maximum; Min=minimum

^a Titration step to achieve a dose not previously administered^b Titration step subsequent to a back-titration

Note: Asymmetrical dosing with no more than 50mg difference between morning and evening doses will be allowed for subjects taking tablets who require back-titration in a 50mg increment (ie, only 50mg and 100mg tablets are available)

There is no limit to the number of back-titration steps or dose holds allowed and all are at the investigator's discretion; however, subjects must achieve the minimum LCM target dose for their body weight category by the end of the Titration Period. If it becomes apparent that a subject will not be able to reach the minimum target dose, then the subject should be withdrawn from the Titration Period and enter the Taper Period.

Subjects who have LCM titrated to a higher dose not previously administered should remain at that dose for ≥7 days unless a back-titration step is required based on tolerability. Subjects who have LCM back-titrated must remain on the lower dose for ≥3 days (in order to reach steady state) before a subsequent dose increase. After back-titration, subjects who return to a higher dose previously administered must maintain that dose for ≥3 days before subsequent titration to a higher dose.

As outlined in Table 7-3, subjects will be required to achieve and maintain at least a minimum LCM dose for at least the final 3 days of Week 6 to be eligible for entry into the Maintenance Period. Subjects may have a back-titration step as late as the last day of Week 6, as long as the minimum target dose is maintained.

Table 7–3: Required LCM dose for at least the final 3 days of Week 6

Body weight category (formulation)	LCM for at least the final 3 days of Week 6	
	Minimum	Maximum
<50kg (oral solution)	4mg/kg/day	12mg/kg/day
≥50kg (tablets/oral solution)	200mg/day	600mg/day

LCM=lacosamide

Eligible subjects (those who reach and maintain at least the minimum LCM dose for at least the final 3 days of the Titration Period) will enter a 12-week Maintenance Period at the dose they achieved at the last day of Week 6. The LCM dose will remain stable throughout the Maintenance Period. Subjects who require a change in dose during the Maintenance Period

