will be withdrawn from the study. Subjects who require a change in formulation during the Maintenance Period should consult the medical monitor to assess if the subject can continue in the study. Subjects may be eligible for participation in the additional open-label study (SP848) if they have completed the Maintenance Period and are taking a minimum dose of 4mg/kg/day for subjects weighing <50kg, and 200mg/day (tablets/oral solution) for subjects weighing ≥50kg. Subjects will begin SP848 on the LCM dose they were taking in the Maintenance Period in SP0966. Subjects who do not complete the full 12 weeks of the Maintenance Period may still be eligible to enter the SP848 open-label study after consultation with the medical monitor.

Subjects who choose not to participate in the open-label study or subjects who discontinue due to other reasons will enter a 2- to 4-week Taper Period followed by a Safety Follow-Up Visit 2 weeks (±2 days) after the final dose of LCM and a Safety Follow-Up Telephone Contact 30 days (-1/+3 days) after the final dose of LCM. The doses to be used during the Taper Period and the duration of the Taper Period will depend on the dose maintained during the Maintenance Period.

Table 7-4 and Table 7-5 display the recommended LCM dose reductions during the Taper Period for subjects <50kg and ≥50kg, respectively. A slower taper is permitted if medically necessary. Whenever possible, these cases should be discussed with the medical monitor prior to withdrawing the subject from the study, especially in cases in which exit criteria have been met. In case of an emergency, a faster taper is permitted after discussion with the medical monitor, whenever possible. Taper of LCM may not be required for some subjects who discontinue study medication prematurely, depending on the treatment option selected by the investigator in consultation with the subject and/or parent/legal representative.

Table 7-4: Recommended LCM dose taper for subjects <50kg receiving oral solution formulation

Maximum LCM dose achieved	Taper schedule			
	Week 19	Week 20	Week 21	Week 22
11-12mg/kg/day	9mg/kg/day	6mg/kg/day	4mg/kg/day	2mg/kg/day
9-10mg/kg/day	8mg/kg/day	6mg/kg/day	4mg/kg/day	2mg/kg/day
7-8mg/kg/day	6mg/kg/day	4mg/kg/day	2mg/kg/day	2mg/kg/day
5-6mg/kg/day	4mg/kg/day	2mg/kg/day	2mg/kg/day	NA
3-4mg/kg/day	2mg/kg/day	2mg/kg/day	NA	NA

LCM=lacosamide; NA=not applicable (taper not required)

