Note: Subjects with doses <3mg/kg/day do not need to taper. End of Taper Visit will be at the end of Week 22 for subjects undergoing 4 weeks of taper, at the end of Week 21 for subjects undergoing 3 weeks of taper, and at the end of Week 20 for subjects undergoing 2 weeks of taper.

Note: Subjects not requiring taper will enter directly into the Safety Follow-Up Period and not attend any Taper Period visits.

Note: The study week numbers provided are for subjects who complete the Maintenance Period and enter the Taper Period. The study week numbers provided do not apply to subjects who enter the Taper Period at other times.

Table 7–5: Recommended LCM dose taper for subjects ≥50kg receiving oral solution or tablet formulation

Maximum LCM dose maintained	Taper schedule			
	Week 19	Week 20	Week 21	Week 22
550-600mg/day	500mg/day	300mg/day	200mg/day	100mg/day
450-500mg/day	400mg/day	300mg/day	200mg/day	100mg/day
350-400mg/day	300mg/day	200mg/day	100mg/day	100mg/day
250-300mg/day	200mg/day	100mg/day	100mg/day	NA
150-200mg/day	100mg/day	100mg/day	NA	NA

LCM=lacosamide; NA=not applicable (taper not required)

Note: Subjects with doses <150mg/day do not need to taper. End of Taper Visit will be at the end of Week 22 for subjects undergoing 4 weeks of taper, at the end of Week 21 for subjects undergoing 3 weeks of taper, and at the end of Week 20 for subjects undergoing 2 weeks of taper.

Note: Subjects not requiring taper will enter directly into the Safety Follow-Up Period and not attend any Taper Period visits.

Note: The study week numbers provided are for subjects who complete the Maintenance Period and enter the Taper Period. The study week numbers provided do not apply to subjects who enter the Taper Period at other times.

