8.4.1 Taper Period

For subjects who do not enroll in the open-label study (SP848), a 2- to 4 week (depending on dose achieved) Taper Period will be scheduled. For subjects completing the full duration of the Maintenance Period, the Taper Period will begin at Week 19 (±2 days). For subjects who do not complete the full duration of the Maintenance Period, the Taper Period will begin earlier, at the time that they end the Maintenance Period. Please refer to Section 7.2 for details of the taper schedule. Taper of LCM may not be required for some subjects who discontinue study medication prematurely, depending on the treatment option selected by the investigator in consultation with the subject and/or parent/legal representative. These subjects should complete Visit 9/Early Termination Visit and then complete the Safety Follow-Up Visit 2 weeks (±2 days) after the final dose of LCM and a Safety Follow-Up Telephone Contact 30 days (-1/+3 days) after the final dose of LCM.

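### Table 7-4 selects the under-50 kg taper by the maximum dose achieved, but Section 7.2 and Table 7-5 use the dose maintained; after back-titration the two can give different taper doses and lengths

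*Protocol*

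**What the plan says.** Two dose bases are in use for the taper.

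- **Maintained.** The Section 7.2 sentence leading into both tables says that the doses and duration of the taper "will depend on the dose maintained during the Maintenance Period". Table 7-5 (50 kg and over) is headed "Maximum LCM dose maintained".
- **Achieved.** Table 7-4 (under 50 kg) is headed "Maximum LCM dose achieved". Section 8.4.1 gives the taper length as "depending on dose achieved) Taper Period will be scheduled". Section 8.4.1.2 and Table 5-1 footnote f tie the End of Taper week to the dose level achieved and point to both tables.

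Section 7.2 describes the tables' purpose in one phrase: they "display the recommended LCM dose reductions during the Taper Period".

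The titration rules allow the two doses to part. Section 7.2 states that "There is no limit to the number of back-titration steps or dose holds allowed". The Table 7-2 columns "Dose decrease per back-titration step" allow 1 to 2 mg/kg/day per step under 50 kg. Timing is also open: "Subjects may have a back-titration step as late as the last day of Week 6", provided the minimum of 4 mg/kg/day is kept. The dose on that day is then held fixed through Maintenance.

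**The concern.** A child who is back-titrated has a peak dose above the dose carried into Maintenance. Taken at its word, the Table 7-4 heading selects the row by the peak, while the sentence leading into it selects the row by the lower dose. A site following the heading could start the taper at or above the dose being taken, in a child who had stepped down because of tolerability. Two sites could also give different tapers to children with identical dosing histories.

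Subjects withdrawn during Titration are a further gap. Section 7.2 sends those who cannot reach the minimum dose into the Taper Period, but they have no maintained dose. Section 8.4.1 starts an early taper when the subject ends Maintenance, which these subjects never entered. The Table 7-4 note exempting doses below 3 mg/kg/day does not say which dose is meant.

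**Working it through.** **Inputs.** Table 7-4 rows (Weeks 19 to 22), planned weekly doses (Table 7-1), step size (Table 7-2) and minimum Maintenance dose (Table 7-3).

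| Row (mg/kg/day) | Taper doses | Weeks |
|---|---|---|
| 11-12 | 9, 6, 4, 2 | 4 |
| 9-10 | 8, 6, 4, 2 | 4 |
| 7-8 | 6, 4, 2, 2 | 4 |
| 5-6 | 4, 2, 2 | 3 |
| 3-4 | 2, 2 | 2 |

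**1. The table where the two bases coincide.** For a child never back-titrated, peak and maintained dose are the same. For doses 3, 4, ..., 12 the Week 19 dose is 2, 2, 4, 4, 6, 6, 8, 8, 9, 9, which is below the dose being taken in all 10 cases. The table then works as a reduction.

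**2. The two bases after back-titration.** Take planned peaks of 6, 8, 10 and 12 and whole-number maintained doses from 4 up to one below the peak. That gives 2 + 4 + 6 + 8 = 20 pairs. Compare the Week 19 dose in the peak's row with the maintained dose.

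| Peak | Week 19 dose | Above current | Equal | Below |
|---|---|---|---|---|
| 6 | 4 | none | 4 | 5 |
| 8 | 6 | 4, 5 | 6 | 7 |
| 10 | 8 | 4, 5, 6, 7 | 8 | 9 |
| 12 | 9 | 4, 5, 6, 7, 8 | 9 | 10, 11 |
| Pairs | | 11 | 4 | 5 |

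The three right-hand columns list the maintained doses concerned. Selected by the peak, the first taper week is no reduction in 11 + 4 = 15 of 20 pairs. Selected by the maintained dose, it is a reduction in all 20 (step 1). Taper length differs between the bases in 10 of 20: peak 6 with maintained 4, and peaks 8, 10 and 12 with maintained 4, 5 or 6. These are counts of possible pairs, not frequencies.

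**3. A permitted path.** Doses of 2, 4, 6 and 8 in Weeks 1 to 4, then steps to 6 and 4 in Weeks 5 and 6, maintained at 4. Achieved (8): 6, 4, 2, 2 over 4 weeks, so Week 19 is 6 against a current 4 (6/4 = 1.5). Maintained (4): 2, 2 over 2 weeks.

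**4. How many steps it takes.** One full 2 mg/kg/day step from a planned even peak: 12 to 10 gives Week 19 = 9 (below); 10 to 8 gives 8, 8 to 6 gives 6, and 6 to 4 gives 4 (all equal). One step therefore never puts Week 19 above the current dose; at least two are needed. An odd peak is possible after an earlier 1 mg/kg/day step-down, and one further step is then enough: 9 to 7 gives 8, and 7 to 5 gives 6.

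**5. Subjects withdrawn in Titration.** Peak 4, stepped back to 2: the row for the dose achieved gives two weeks at 2; the exemption for doses under 3 gives no taper.

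**6. What moves downstream.** In step 3 the taper ends in Week 22 or Week 20, a difference of 4 - 2 = 2 weeks; across the pairs that differ it is one or two weeks. The End of Taper Visit moves with it. SAP 3.2.1 includes the taper in the last dose, and SAP 8.2.2 runs the TEAE window to 30 days after that dose, so the window's end moves equally. By contrast, SAP 8.4 summarizes exposure for the Treatment, Titration and Maintenance Periods, and SAP 3.2.3 ends the Treatment Period at Visit 9/ET. Seizure days and EEG counts also stop by Visit 9/ET.

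**The case against.** The best case for the plan is that *achieved* is loose wording for the dose carried forward. Section 7.2 uses it for the dose on the last day of Week 6, after any back-titration, and the Figure 5-2 notes use it for the dose taken in Maintenance. The text beside the tables names the maintained dose and calls the schedules recommended reductions, and an increase is not a reduction. Slower or faster tapers are allowed. Figure 5-1 could not be read in the copy reviewed, so whether it settles the basis is unchecked. This makes a harmless intent plausible. It does not remove the conflict: the heading pairs *achieved* with *maximum*, which reads as the peak, and flexibility of pace does not tell a site which row to start from.

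Three stronger readings are tempting, and the documents do not support them.

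- A reader might take the widest gaps as typical. Peak 12 with maintained 6 gives 9 in Week 19 (9/6 = 1.5), and peak 12 with maintained 4 also gives 9 (9/4 = 2.25). But 12 is reached only in Week 6 under Table 7-1, so these paths need at least three and four step-downs within about the last week of Titration. They are permitted, but extreme.
- A reader might infer that the planned exposure summaries are affected. They end before the taper. The TEAE window does move, but it is anchored to each subject's actual last dose and already varies with taper length.
- A reader might take the running text as uniformly on the maintained dose, with Table 7-4 the only exception. Only Section 7.2 and Table 7-5 use that basis.

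Withdrawal during Titration is partly covered: the table notes say that the week numbers do not apply to subjects tapering at other times, and Sections 7.2 and 8.4.1 allow some subjects to omit the taper. Which dose selects the row remains unstated.

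**Conclusion.** The concern holds as an internal contradiction in a dosing instruction, present in the current protocol text. For a back-titrated child under 50 kg, a literal reading of Table 7-4 can give a first taper-week dose equal to the dose being taken after one full step from a planned peak of 6, 8 or 10 mg/kg/day. It can give a higher dose after two or more steps. Taper length, the End of Taper Visit and the end of the TEAE window can move by one or two weeks. The planned exposure summaries and the seizure and EEG variables are unaffected.

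This rests on reading *maximum achieved* as the titration peak and on whole-number doses. It concerns only back-titrated subjects who taper; subjects entering SP848 do not. The documents do not say how many that will be, so no frequency is claimed. Nor is any view taken on which dose basis is clinically right.

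**What to change.** Reconcile the headings of Tables 7-4 and 7-5, the Section 7.2 sentence leading into them, Sections 8.4.1 and 8.4.1.2, and Table 5-1 footnote f, so that all name one defined dose basis. State which basis applies to subjects withdrawn during Titration, and which dose the no-taper threshold refers to. The clinical team must decide the basis. The cost is wording in a protocol clarification or amendment and a clarification to sites; no planned analysis in the SAP has to change.

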7.3 Packaging

Lacosamide is manufactured, packaged, and labeled according to Good Manufacturing Practice (GMP) guidelines and applicable laws or regulations. It is suitably packaged in such a way as to protect the product from deterioration during transport and storage.

Lacosamide tablets will be packaged in high-density polyethylene bottles with a child-proof polypropylene screw cap. The oral solution will be packaged in amber polyethylene terephthalate bottles with a white, child-proof, polypropylene screw cap.

7.4 Labeling

Clinical drug supplies will be labeled in accordance with the current ICH guidelines on Good Clinical Practice (GCP) and GMP and will include any locally required statements. If necessary, labels will be translated into the local language.

7.5 Handling and storage requirements

The investigator (or designee) is responsible for the safe and proper storage of IMP at the site. Investigational medicinal product stored by the investigator is to be kept in a secured area with limited access.

Lacosamide is to be stored according to the instructions on the label. Lacosamide is stable at room temperature and is to be stored at temperatures not exceeding 25°C (77°F). Lacosamide should not be refrigerated or frozen.

Appropriate storage conditions must be ensured either by controlled room temperature, or by completion of a temperature log (showing minimum and maximum temperatures reached over the time interval) in accordance with local requirements on a regular basis. Data should

be available to support the temperature conditions maintained at the clinical site (eg manual temperature logs or automated chart recordings).

In case an out of range temperature is noted, it must be immediately communicated to the sponsor's designee in accordance with the pharmacy manual.

The investigator (or designee) will instruct the subject to store the IMP following the instructions on the label.

7.6 Drug accountability

A Drug Accountability form will be used to record IMP dispensing and return information on a by-subject basis and will serve as source documentation during the course of the study. Details of any IMP lost (due to breakage or wastage), not used, or returned to the sponsor's designee must also be recorded on the appropriate forms. All supplies and pharmacy documentation must be made available throughout the study for UCB (or designee) to review.

The investigator (or designee) is responsible for retaining all used, unused, and partially used containers of IMP until returned.

The investigator may assign some of the investigator's duties for drug accountability at the study site to an appropriate pharmacist/designee.

The investigator must ensure that the IMP is used only in accordance with the protocol.

Periodically, and/or after completion of the clinical period of the study, all used (including empty containers) and unused IMP containers must be reconciled and returned to UCB's designee, preferably in their original package. Investigational medicinal product intended for the study cannot be used for any other purpose than that described in this protocol.

7.7 Procedures for monitoring subject compliance

At each visit after IMP is dispensed, subjects must return all used, unused, and empty IMP containers. Drug accountability must be done in the subject's presence in order to obtain explanations regarding discrepancies in compliance with the dosing regimen. Drug accountability must be recorded on the Drug Accountability form.

If a subject is found to be persistently noncompliant (defined as <75% or >125% compliant with the dosage schedule), the sponsor, in conjunction with the investigator, will make a decision as to whether the subject should be withdrawn from the study.

7.8 Concomitant medication(s)/treatment(s)

7.8.1 Permitted and prohibited concomitant treatments (medications and therapies)

Subject must have been maintained on a stable dose regimen of 1 to 3 marketed AEDs for at least 4 weeks prior to Visit 1 (ie, prior to entry into the Baseline Period); the dose regimen of the AEDs must be kept stable through the end of the Maintenance Period.

Vagal nerve stimulation is allowed and will not be counted as a concomitant AED. The VNS device must be implanted for at least 6 months before Visit 1, and the device settings must be

stable for at least 4 weeks before Visit 1 and be kept stable during the Baseline Period and through the end of the Maintenance Period.

The following medications/therapies are prohibited during the course of this study:

- Neuroleptics
- MAO inhibitors
- Barbiturates (except as anti-epileptic medications)
- Narcotic analgesics

Subjects who have been treated with vigabatrin and experienced any vision loss are excluded from the study. Subjects who have received vigabatrin in the past must have documentation of an assessment for vision loss prior to study entry or documentation of why visual field testing cannot be performed.

Subjects who have been treated with felbamate and have experienced any serious toxicity issues (defined as liver failure, aplastic anemia) with this treatment are excluded from the study. Subjects treated with felbamate for less than 12 months are also excluded. Any subject who has been treated with felbamate for at least 12 months and has not experienced serious toxicity issues is eligible for the study.

The following medications are not allowed unless used as described:

- Amphetamines and sedative antihistamines: stable use only.
- Anxiolytics or once-daily hypnotics: stable, low doses are allowed for nonepilepsy indications only.

The chronic use of benzodiazepines is allowed for treatment of epilepsy. Benzodiazepines taken for treatment of epilepsy will be counted as 1 of the AEDs, and the dose regimen must be stable for ≥ 28 days prior to Visit 1. Intermittent use of benzodiazepines as rescue therapy for epilepsy is allowed if taken at a maximum frequency of 1 day per week (with up to 3 doses within 24 hours).

Therapy that becomes necessary (in the investigator's opinion) during the course of the study must not be refused to a subject, even if described above as a therapy that is expressly not permitted. In cases where this occurs but withdrawal criteria have not been met, the advisability of the subject's continuation in the study must be discussed between the medical monitor and the investigator.

